Hyperoxia also induces vasoconstriction,¹⁹⁻²⁰ and ROS impair endothelial function.²¹ For example, pigs exposed to hyperoxia produced less endothelial-derived NO and had increased vasoconstriction compared to controls, and in humans hyperoxia-induced vasoconstriction is prevented by antioxidant treatment, indicating that the vasoconstriction effect of hyperoxia is at least partially mediated by ROS.²²⁻²³ These effects impair tissue perfusion and may be integral to development of postoperative organ injury. Therefore, endothelial function secondary to hyperoxia, secondary to oxidative stress, or independent from oxidative stress may be an important contributor to kidney, brain, and heart injury following cardiac surgery. The ROCS trial provides an ideal framework to test these hypotheses based on the ROCS trial population for the study, randomized oxygen treatments, detailed hemodynamic, perfusion, and oxygenation characterization, blood and tissue sampling, and outcomes assessments.

To test the hypotheses that physiologic oxygenation during cardiac surgery improves endothelial function compared to hyper-oxygenation (sub-study Aim 1), that endothelial dysfunction correlates with oxidative stress in patients having cardiac surgery (sub-study Aim 2), and that perioperative endothelial dysfunction is associated with organ injury (sub-study Aim 3) we will measure endothelial function at baseline (pre-intervention) and following cardiac surgery and compare these measurements between randomized oxygenation groups and to the ROS, F₂-isoprostanate/isofuran, oxygenation, and outcomes data generated in the ROCS trial. We will assess endothelial function at baseline and following surgery by quantifying brachial artery flow mediated dilation (FMD), performing peripheral arterial tonometry to

determine reactive hyperemia index, measuring endothelium-dependent and independent vasodilation in epicardial fat arterioles and distal mammary artery segments *ex vivo* using wire myography, and measuring markers of endothelial activation (E-selectin and plasminogen activator inhibitor [PAI]-1) in blood.

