10.0 Statistical Analysis Plan

The primary objective of the analysis will be to compare the effect of intraoperative oxygenation on oxidative damage and organ injury. The primary endpoint of Aim 1 will be change in serum creatinine from baseline (defined as the most recent creatinine measured prior to surgery) to postoperative day 2. The primary endpoint of Aim 2 will be F₂-isoprostanes/isofurans measured in plasma.

Sample Size Calculations

We calculated the subject sample size based on data from the Vanderbilt Statin AKI Cardiac Surgery RCT (PI: [name]).²⁷ Data from this study indicate that mean serum creatinine concentrations increase 0.08 ± 0.37 mg/dl from baseline to postoperative day 2. We have powered the present randomized clinical trial conservatively, particularly since consensus criteria for AKI diagnosis define AKI as a 0.3 mg/dl rise in serum creatinine from baseline to postoperative day 2.²⁹ With 200 subjects, we will have 80% power to detect a 0.15 ± 0.375 mg/dl difference in serum creatinine between groups, with a type I error rate of 5%. In addition, with 200 subjects we will have 80% power to detect a 20 ± 50 pg/ml difference in plasma F₂-isoprostanes between groups, and we observed that physiologic oxygenation was associated with 35 ± 30 pg/ml less increase in plasma concentrations of F₂-isoprostanes among pilot subjects compared to hyper-oxygenated subjects. To account for a potential dropout rate of 10%, we plan to recruit 222 subjects.

For the endothelial function sub-study, we calculated the sample size based on a prior study of patients administered an oral antioxidant, treatment improved FMD 2.3% more than placebo with a standard deviation of 2.0%.³⁰ With 80 patients, we will have greater than 80% power to detect a 2%

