difference in FMD change from baseline to ICU admission between subjects randomized to hyper-oxygenation vs. physiologic oxygenation with a standard deviation of 3.0%, with a type I error rate of 0.05 (primary analysis sub-study Aim 1). We will have 94% power to detect a correlation of 0.2 or greater between intraoperative F₂-isoprostan concentrations and postoperative FMD (primary analysis sub-study Aim 2) with standard deviation of 20 pg/ml F₂I and 10 for regression errors. We will have greater than 80% power to detect a 2% difference in FMD between patients who do and do not develop postoperative delirium in the ICU, assuming a delirium incidence of 23.4% among all ROCS trial subjects, similar to that in the Statin AKI Cardiac Surgery RCT. Sub-study Aims 1 and 2 will be completed with 80 ROCS trial subjects and sub-study Aim 3 with all 200 patients.

Randomization

The study's statistician will be responsible for centralized randomization and subject assignment based on stratification in a permuted block fashion, using a sequence of blocks with sizes either two or four, where the sizes are selected uniformly at random. Randomization will be stratified by chronic kidney disease (defined as stage 3, 4, or 5 CKD [i.e., an eGFR <60 ml/min/1.73m²]) and use of cardiopulmonary bypass during surgery. Thus, there will be four randomization strata. We use the modification of diet in renal disease formula to estimate GFR for randomization stratification. This scheme provides ample subject assignment to all strata.

Data Analysis Plan

Standard graphing and screening techniques will be used to evaluate data quality. Data include patient demographics, baseline and intraoperative clinical characteristics, treatment toxicity and clinical outcomes. Summary statistics of study arms for both numerical and categorical variables will be provided to describe the study sample. Continuous variables will be summarized with the 50th (10th, 25th, 75th, 90th) percentiles, mean and standard deviation, and categorical variables will be summarized with the counts and percentages. For outcomes measured at a single time point, comparisons across randomization groups will be implemented using the Fisher's exact test or Pearson chi-square test for categorical variables, and the Wilcoxon rank sum test or Student T-test for quantitative outcomes, as appropriate. The Clopper-Pearson and Wald methods will be used to construct 95% confidence intervals for the between group effects.

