ischemic attack, and stroke between treatment groups. Similar to the primary analysis, we will implement logistic, proportional odds and linear regression analyses for binary, ordinal or highly skewed, and continuous outcomes, respectively, using a propensity score adjusted approach, if warranted. Potential impactful covariates included in these models will be specific to each outcome (for example, history of chronic obstructive pulmonary dysfunction would be appropriate covariate for time to extubation analysis).

To test the hypothesis (Endothelial function sub-study) that intraoperative physiologic oxygenation improves postoperative endothelial function (sub-study Aim 1) we will compare change from baseline in FMD (primary endpoint of Endothelial function sub-study), reactive hyperemia index, PAI-1, and E-selectin and the amplitude of endothelium-dependent vasodilation randomized subject groups in the first 80 subjects to complete the ROCS trial. The change from baseline in FMD, RHI, PAI-1, and E-selectin and the amplitude of endothelium-dependent vasodilation will be compared between oxygenation groups using Student's t-test or Mann Whitney U test. To test the hypothesis that endothelial dysfunction correlates with increased oxidative stress during cardiac surgery (sub-study Aim 2) we will compare perioperative concentrations of F₂-isoprostanes and isofurans to endothelial function assessments and plasma markers of endothelial activation at ICU admission in the first 80 subjects to complete the ROCS trial using linear regression and adjust for baseline measurements of endothelial function, and confounders such as randomized treatment group, blood transfusion, and duration of CPB. To test the hypothesis that perioperative endothelial dysfunction is associated with organ injury (sub-study Aim 3) we will compare baseline, postoperative, and change from baseline FMD, reactive hyperemia index, PAI-1, and E-selectin and the amplitude of endothelium-dependent vasodilation to markers of AKI, delirium, myocardial injury, and additional secondary endpoints using logistic, linear, or proportional odds regression as appropriate in the total cohort (N=200). We will review, interpret, and report results from sub-study Aims 1 and 2 based on statistical report from [name] but will remain blinded to treatment assignments in these 80 subjects until the entire 200 patient cohort is completed.

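### The sub-study's primary comparison of change in FMD does not adjust for baseline FMD: valid and powered as stated, but it may give up precision at almost no saving

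*Combined protocol and SAP*

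**What the plan says.** The endothelial sub-study text in section 2.0 provides the baseline value: "we will measure endothelial function at baseline (pre-intervention) and following cardiac surgery".

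Section 10.0, Sample Size Calculations, powers the sub-study on the change score, described there as the "difference in FMD change from baseline to ICU admission between subjects" in the two arms. Its inputs are 80 patients, a target of 2%, an SD of 3.0% and a type I error of 0.05, for which it claims power above 80%.

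Section 10.0, Data Analysis Plan, names the same quantity as the endpoint, "we will compare change from baseline in FMD (primary endpoint of Endothelial function sub-study". For FMD, reactive hyperemia index (RHI), PAI-1 and E-selectin, the change from baseline "will be compared between oxygenation groups using Student's t-test or Mann Whitney U test". No covariate is named for this comparison. For sub-study Aim 2, in the same 80 patients, the plan models endothelial function at ICU admission "using linear regression and adjust for baseline measurements of endothelial function".

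The only other text on covariates is the regression sentence that closes the preceding paragraph. It belongs to the main trial's secondary and safety endpoints, and its propensity-score option is conditional. It does not supply a baseline-adjusted FMD analysis.

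**The concern.** Subtracting baseline uses the baseline value, but with a slope fixed at 1. If the true slope of post-surgery FMD on baseline FMD is not 1, the subtraction leaves avoidable noise in the outcome. If by chance one arm starts with higher FMD, part of that difference also carries into the contrast through regression to the mean. Randomisation is stratified by chronic kidney disease and bypass use, not by FMD, so with about 40 patients per arm some imbalance is to be expected.

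A linear model with baseline FMD as a covariate (ANCOVA) estimates the slope instead. In large samples its variance is never higher than that of the change score. What is at stake is the width of the confidence interval for the sub-study's primary result and how far that result depends on the luck of the baseline draw.

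**Working it through.** **Inputs from section 10.0.** Difference 2 (read as FMD percentage points); SD of change 3.0; 80 patients; two-sided alpha 0.05.

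**Assumptions.** 40 per arm (the ratio is not stated; two arms in blocks of two or four are read as 1:1). The correlation ρ between baseline and post-surgery FMD, and the ratio k = post-surgery SD / baseline SD, are not in the documents, so both are varied. The SD of change is held at the plan's 3.0 throughout.

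**Step 1: the plan's own figure.** Standard error = 3.0 × √(2/40) = 0.671. Noncentrality = 2/0.671 = 2.98. Noncentral t with 78 df: power 83.8%. For Mann Whitney under normality (efficiency 3/π), about 82%. Both agree with the stated figure of more than 80%.

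**Step 2: the adjusted model.** With baseline variance s²:
- variance of change = s²(1 + k² − 2ρk) = 9
- ANCOVA residual variance = k²s²(1 − ρ²)
- ratio of the two = k²(1 − ρ²)/(1 + k² − 2ρk)

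With k = 1 the ratio is (1 + ρ)/2, so the residual SD is 3.0 × √((1 + ρ)/2). When the slope ρk equals 1 the ratio is 1 and there is no gain.

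**Step 3: equal SDs (k = 1), 40 per arm, 77 df.**

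| ρ | Residual SD | Power | Patients for the precision of 80 on the change score: 80 × (1 + ρ)/2 |
|---|---|---|---|
| 0.3 | 2.42 | 95.5% | 52 |
| 0.5 | 2.60 | 92.5% | 60 |
| 0.7 | 2.77 | 89.1% | 68 |
| 0.9 | 2.92 | 85.6% | 76 |

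A simulation with 6,000 runs per value gave 95.5%, 92.0% and 89.0% for the first three rows.

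**Step 4: unequal SDs, same formulae.**

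| k | ρ | Slope ρk | Residual SD | Power |
|---|---|---|---|---|
| 0.7 | 0.5 | 0.35 | 2.05 | 99.1% |
| 0.7 | 0.7 | 0.49 | 2.10 | 98.8% |
| 1.1 | 0.9 | 0.99 | 3.00 | 83.8% |
| 1.2 | 0.7 | 0.84 | 2.95 | 85.0% |
| 1.3 | 0.7 | 0.91 | 2.99 | 84.1% |
| 1.5 | 0.7 | 1.05 | 3.00 | 83.8% |
| 1.5 | 0.9 | 1.35 | 2.64 | 91.6% |

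The gain over 83.8% is 0 to about 1 point where the slope is near 1, and grows as the slope moves away from 1 in either direction. With the slope exactly 1, the lost degree of freedom costs about 0.01 points of power.

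**Step 5: chance imbalance (k = 1).** Given an observed baseline difference D, the change-score contrast is displaced by (1 − ρ)D in size, against the arm that started higher. Baseline SD = 3.0/√(2(1 − ρ)) = 2.54, 3.00 and 3.87 at ρ = 0.3, 0.5 and 0.7. The standard error of D is that SD × √(2/40) = 0.567, 0.671 and 0.866. A one-standard-error imbalance moves the estimate by 0.40, 0.34 or 0.26 FMD points, and two standard errors by 0.79, 0.67 or 0.52, against a 2-point target. Adjustment removes this displacement.

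**The case against.** The best defence is that nothing in the plan fails. Under randomisation the change-score comparison is unbiased over repeated trials and holds its type I error, and its standard error already allows for chance imbalance. The quantity that was powered is the quantity that is tested, and the stated power reproduces. All of this stands. A reader might infer that the planned test is biased or underpowered; the documents support neither. The displacement in Step 5 is conditional on a given imbalance and is not a bias of the method.

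A reader might also take the different handling of Aims 1 and 2 as an inconsistency. It is not one. Aim 2 is an observational association, and the plan adjusts there for baseline alongside confounders such as transfusion and bypass duration. Randomisation deals with confounding in Aim 1. The contrast shows only that the covariate is available and already in use.

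Third, the benefit rests on two unknowns. This also stands. The equal-SD figures (52 to 76 patients doing the work of 80) should not be read as an expected saving, because a plausible SD ratio above 1 can remove nearly all of it.

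Finally, a linear model gives up the rank test, which is the plan's provision for skewed data. That is a reason to keep the rank test as a sensitivity analysis. It does not remove the case for adjustment. The sub-study text gives no rule for choosing between its two tests, and the documents give no distribution for PAI-1 or E-selectin that would justify fixing a transformation now.

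**Conclusion.** The point holds as an efficiency gain of uncertain size, not as an error. The planned test is valid and meets its stated power (83.8% by t-test). Adding baseline FMD would raise power to between 85.6% and 95.5% with equal SDs and ρ from 0.9 down to 0.3, and to about 99% with an SD ratio of 0.7. It would add 0 to about 1 point where the slope ρk is close to 1, for example an SD ratio of 1.2 or 1.3 with ρ = 0.7. These figures assume 40 per arm, an SD of change of 3.0 and normal errors; ρ and the SD ratio are assumptions throughout. The benefit may be negligible or large, while the most that adjustment can be expected to lose is one degree of freedom. That asymmetry is the reason to change the plan.

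**What to change.** Make the sub-study Aim 1 primary analysis a linear model of FMD at ICU admission on randomised arm and baseline FMD, and report the adjusted difference with its 95% CI. Use the same baseline adjustment for RHI, PAI-1 and E-selectin, with any transformation chosen on blinded data. Keep the planned change-score t-test or Mann Whitney U test as a sensitivity analysis. Leave the myography amplitude as a two-group comparison: it is measured on tissue removed at surgery, and no pre-intervention value is described.

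The cost is a sentence or two of SAP wording and one degree of freedom. No new data are needed, and no patients are lost relative to the present plan, because the change score needs the baseline value too. A single named primary model also settles the open choice between the two tests and directly gives the estimate and interval that section 10.0 promises.

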Study anesthesiologists and perfusionists will be responsible for protocol-directed administration of hyper- or physiologic oxygenation. Therefore, anesthesiologists and perfusionists will be aware of subject treatment assignment. We do not expect knowledge of treatment assignment by anesthesiologists or perfusionists to affect other aspects of intraoperative management, including medication or fluid administration. We expect subjects randomized to physiologic oxygenation or hyper-oxygenation to behave the same (similar vital signs, similar responses to surgery, similar response to medications, etc.) and to not warrant any differences in care based on treatment assignment. Operating room surgeons will not be informed of subject assignment, but we will not initiate any procedures such as concealing oxygen and air flow meters to actively blind them from assignment. We do not expect any knowledge of subject treatment assignment by surgeons to affect their treatment of subjects. Study subjects, ICU nurses, intensivists, laboratory technicians, and statisticians will be blinded to treatment assignment throughout subject study. To ensure blinding of ICU intensivists and staff, anesthesiologists will withhold treatment group assignment at the time of subject transfer of care at the end of surgery. Objective endpoints such as laboratory values will be measured by technicians and co-investigators blinded to treatment assignment. Clinical endpoints such as wound infection and delirium will be measured by physicians and research staff blinded to treatment assignment. The key that lists the treatment of each subject will be withheld from investigators, laboratory technicians, and statisticians until the dataset is locked. All preoperative, intraoperative, and postoperative clinical care will be administered according to standardized clinical protocol and will not be affected by inclusion in this study or by study group assignment.

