4. Oxygen administration, tissue oxygenation, and perfusion, specifically SpO₂ (median +/- 95% CI and area-under-the-curve (AUC) < 90%), PaO₂ (median +/- 95% CI, AUC > 150 mmHg, and AUC < 70 mmHg), brain and muscle O₂ saturation (median +/- 95% CI and AUC < 80% baseline), the percent of FIO₂ titrations within protocol (protocol adherence), cardiac output using a PA catheter placed as part of usual care, mixed venous hemoglobin O₂ saturation, and arterial lactate.
5. Oxidative stress. We will measure F₂-isoprostanes/isofurans (Aim 2 primary endpoint) prior to surgery, during surgery, and following surgery.
6. Reactive oxygen species production using electron spin probes and electron paramagnetic resonance and dihydroethidium and HPLC in blood, myocardium, and epicardial fat.
7. Vascular reactivity (Effects on Endothelial Function sub-study). We will measure flow mediated dilation of the brachial artery using ultrasound and peripheral tonometry with wrist or finger probes before and after inflating a blood pressure cuff, and we will measure vasoconstriction and relaxation in blood vessels dissected from epicardial fat and distal mammary artery that is removed and discarded by the surgeon as part of standard cardiac

surgery in a subset of patients chosen at random (n=40). We will quantify markers of endothelial activation in plasma including PAI-1 and E-selectin.

8. Mitochondrial function. We will measure markers of mitochondrial function including superoxide production, mitochondrial DNA content, mitochondrial membrane potential, PGC-1a mRNA expression, and mitochondrial respiration in PBMCs isolated from blood and atrial tissue resected by the surgeon as part of standard cardiac surgery.
9. Other ICU morbidities including the time to extubation, development of arrhythmias including atrial fibrillation, dialysis, pneumonia (defined as a positive sputum culture or postoperative pulmonary infiltrate with systemic signs of infection [temperature >38.6°C or white blood cell count >12.0 × 109/L] and the use of parenteral antibiotics or documentation of the diagnosis by the patient's physician), wound infection (CDC criteria), and ICU length of stay.
10. Pain assessment on postoperative day 5 and at one year, using the Numeric Rating Scale (NRS) 0-10 pain assessment and the short-form McGill Pain Questionnaire.

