Every effort will be made to avoid missing data. Any methods of missing data imputation (e.g. multiple imputation using the chained-equations method) will be used cautiously as sensitivity analyses; and the analysis of results with imputation would be interpreted in the context of corroboration with the analyses without imputation. The primary analysis will be intention-to-treat. Before data unblinding, [name] will examine any protocol deviations and identify a list of protocol violators. In addition to the intention-to-treat analysis, a secondary per-protocol analysis will be conducted.

Specific inferences on the effects of interest will be made by reporting point estimates, along with 95% confidence intervals. Hypotheses will be tested at a two-sided significance level of $\alpha=0.05$. This data analysis plan will be carried out using the statistical analysis package R (R Development Core Team).

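### The between-arm FMD analysis stops at 80 patients although FMD is planned in all 200, and its result would reach investigators before the cohort is complete

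*Combined protocol and SAP*

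**What the plan says.** Section 10.0, Sample Size Calculations, sets the sub-study numbers: "Sub-study Aims 1 and 2 will be completed with 80 ROCS trial subjects and sub-study Aim 3 with all 200 patients". The power statement for sub-study Aim 1 concerns a 2% between-arm difference in FMD change from baseline to ICU admission, "with a standard deviation of 3.0%, with a type I error rate of 0.05 (primary analysis sub-study Aim 1"), with power above 80%.

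The Data Analysis Plan in the same section says how the 80 are chosen. Sub-study Aim 1 (arm comparison of FMD, reactive hyperemia index, PAI-1, E-selectin and vasodilation amplitude) and Aim 2 (regression of endothelial function on F2-isoprostanes and isofurans) are both run "in the first 80 subjects to complete the ROCS trial". Aim 3 relates the same list of measures to organ injury in the total cohort of 200.

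The paragraph ends by saying that the investigators will interpret and report Aims 1 and 2, "but will remain blinded to treatment assignments in these 80 subjects until the entire 200 patient cohort is completed".

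Three other places bear on this:
- Section 5.0 says the treatment key "will be withheld from investigators, laboratory technicians, and statisticians until the dataset is locked".
- Section 6.0, under the DSMB, plans interim looks after 20 and after 100 patients have been studied and discharged. Its conditional power analysis uses arms coded A and B.
- Section 6.0, endpoint 7, places the blood-vessel work "in a subset of patients chosen at random (n=40").

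**The concern.** FMD change is the sub-study's primary endpoint, and its arm comparison is the sub-study's only randomised test of the oxygen intervention on that endpoint. If FMD is measured in 200 patients for Aim 3, limiting the randomised comparison to 80 gives a wider interval than the planned data allow. The plan gives no reason for the limit.

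The second issue is timing. A promise to stay blinded until the 200-patient cohort is finished only makes sense if the report comes earlier. Withholding individual assignments does not hide an arm-level effect. Sub-study Aim 1 tests a directional hypothesis, which is hard to interpret without knowing which arm is which, and even a coded report shows the size of the difference. What is at stake is the blinding and conduct of an ongoing trial in which, by Section 5.0, the anesthesiologists and perfusionists who deliver the intervention already know assignments.

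**Working it through.** **Inputs**
- Target difference in FMD change 2%, SD 3.0%, alpha 0.05, total 80: Section 10.0, Sample Size Calculations.
- Two-sided testing: Section 10.0, Data Analysis Plan ("Hypotheses will be tested at a two-sided significance level of" 0.05).
- Allocation 1:1: inferred from two arms and block sizes of two or four; the ratio is not stated in words. This gives 40 per arm at 80 and 100 per arm at 200.

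**1. Reproduce the plan's figure (80 patients)**

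SE = SD × √(2/n) = 3.0 × √(2/40) = 0.671.

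Power ≈ Φ(2/0.671 − 1.96) = Φ(1.02) = 84.6% by the normal approximation. It is 83.8% for the t-test and about 83.0% for the Mann-Whitney test (relative efficiency 0.955). The stated power above 80% reproduces. The t-test needs 37 per arm, so 40 is enough.

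**2. The same comparison in all 200**

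SE = 3.0 × √(2/100) = 0.424.

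Power ≈ Φ(2/0.424 − 1.96) = Φ(2.75) = 99.7% (also 99.7% for the t-test).

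**3. Precision**

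| Quantity | Formula | 80 patients | 200 patients |
|---|---|---|---|
| Difference detectable with 80% power | (1.96 + 0.84) × SE | 1.88 (t-test 1.90) | 1.19 (t-test 1.19) |
| 95% CI half-width | 1.96 × SE | 1.31 | 0.83 |

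The half-width falls by 1 − √(40/100), about 37%.

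**4. Timing and blinding, side by side**
- The Section 10.0 report on 80 patients is not one of the looks at 20 and 100 in Section 6.0, and no text routes it through the DSMB.
- Section 6.0 codes the arms A and B for its conditional power analysis. Section 10.0 does not say whether the 80-patient report is coded, or who receives it.
- Section 5.0 withholds the key even from statisticians until lock. An arm comparison at 80 needs at least a coded grouping before then.
- The plan does not define completion of the trial. It could mean hospital discharge, as in the interim looks, or the one-year interview (Section 6.0, endpoint 11).

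**5. Ex vivo vessel endpoint**

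Section 2.0 describes endothelium-dependent vasodilation as an ex vivo wire-myography measure. Section 6.0 most naturally places that work in a random 40. Section 10.0 analyses its amplitude in the first 80 and again in 200. If the 40 were read as covering FMD too, it would contradict the 80 and 200 in Section 10.0.

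**The case against.** The best defence is that the sub-study is adequately sized for its stated purpose and that reporting it early has value. The first part stands: 83.8% power meets the target, so 80 is not too few for a 2% difference. Early reporting is a legitimate aim, but it does not explain why no between-arm FMD analysis is planned once the larger data set exists.

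On blinding, the defence is that assignments stay masked, coded reporting is not excluded, and no text sends the report to operating-room staff. FMD is not a main-trial primary endpoint, creatinine is a laboratory value measured by blinded staff, and Section 6.0 excludes stopping for efficacy or futility. All of this stands, and it confines the issue to conduct. It does not remove it, because investigators would still see an arm-level effect size.

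A reader might infer more than the documents support:
- *That the data from the other 120 patients are thrown away.* They are used in sub-study Aim 3, and the treatment effect on F2-isoprostanes is analysed in the main trial.
- *That 120 patients would still be awaiting enrolment, or that the 80 are selected on surviving a year.* These rest on opposite readings of completion. With discharge, the report may fall mid-enrolment but there is no one-year selection. With one-year follow-up, enrolment may be well past 80 or over. No accrual rate is given.
- *That the look feeds the sample-size decision.* Section 6.0 bases that on conditional power for the main-trial primary endpoints; FMD is not an input.
- *That sub-study Aim 2 is underpowered.* The plan's 94% reproduces from its own SDs as a regression slope of 0.2: 0.2 × 20 × √80 / 10 = 3.58, giving 94.2% by the t distribution. Calling that slope a correlation is a separate matter.
- *That sub-study Aim 2 reveals the main Aim 2 result.* Its model has treatment group as a covariate and does not itself estimate the treatment effect on F2-isoprostanes.

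**Conclusion.** The point holds as avoidable loss of precision plus an incompletely protected early result. Using all 200 would raise power for a 2% FMD difference from 83.8% to 99.7%, lower the detectable difference from about 1.9 to 1.2 points, and narrow the CI half-width from about 1.3 to 0.8. These figures assume 1:1 allocation, the plan's SD of 3.0%, and usable FMD measurements in all 200, as Aim 3 requires; missing measurements would reduce the gain.

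That an arm comparison would be seen before the cohort is complete is inferred from the wording of the blinding clause; its calendar timing cannot be established. It fits poorly with Section 5.0 and lies outside the interim looks in Section 6.0. Main-trial type I error is unaffected, and no bias in a main-trial endpoint is demonstrated. The change is worth making because it is cheap, not because the sub-study fails as designed.

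**What to change.** In Section 10.0:
- Make the definitive analysis of sub-study Aims 1 and 2 the one in all randomised patients with the needed baseline and ICU-admission measurements, after database lock. Delete the restriction "in the first 80 subjects to complete the ROCS trial".
- If an 80-patient analysis is kept, define completion and call the analysis preliminary. Keep its arm-level results with the statistician or DSMB until lock, and align Sections 5.0 and 6.0 with that.
- Reconcile the ex vivo vessel endpoint: state whether it is measured in the random 40, in 80 or in 200, and use the same number in Sections 6.0 and 10.0.

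The cost is SAP wording and a later sub-study report. No patients, FMD, tonometry or plasma measurements are needed beyond those already planned for Aim 3.
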